AKI, defined as a sudden decrease in function and damage to kidneys is common among critically ill patients. The creatinine based Kidney Disease Improving Global Outcomes (KDIGO) criteria define AKI as an increase in serum creatinine by 1.5 times the baseline creatinine of by $\geq 0.3\text{mg/dL}$ [2]. The incidence of AKI at 2.1 per 1000 population is similar to that of heart attacks [3]. It is seen in 10-15% of all hospitalized patients but has been described in over 50% of critically ill patients [4, 5]. It has been described to be present among 15-25% patients with COVID-19 [6, 7].

AKI is not only common but is associated with 3-4 times higher mortality [8, 9], development of chronic kidney disease [10], end stage renal disease [11] and increase in healthcare expenditure [12]. There are no definitive therapies for AKI and treatment primarily rests on prevention of progression of AKI and management of its complications such as hyperkalemia, acidosis and volume overload. Approximately 6-13% of critically ill patients develop severe AKI that requires life-saving dialysis therapy [5, 13] but dialysis itself is associated with high mortality [13] and life-threatening complications such as infections. Therefore there is a great interest in developing therapies and treatment approaches that can prevent AKI in critically ill patients.

2. Hypothesis

We hypothesize that alkalization of urine is safe and effective to prevent development of AKI in patients with COVID-19

3. Significance

Although COVID-19 primarily affects the lungs and may cause severe hypoxemia, other organs including the GI tract, heart and kidney are affected. Acute kidney injury secondary to COVID-19 (COV-AKI) is reported to occur in about 15-25% of patients hospitalized with COVID-19 infection. [6, 7] However, AKI was much more common in non-survivors ($>50\%$). The majority of AKI cases are mild to moderate with renal replacement requirement in about 25% of AKI cases. But with COVID-19 taking the form of a pandemic, this has translated into thousands of patients needing dialysis. There are already reports of hospitals running out of dialysis machines to provide life-saving therapy critical for COVID-19 patients with AKI. As such there is a critical need to identify therapies that can delay the development or progression of AKI in these patients. Although kidney failure appears to occur late in the course, patients may begin to

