Thus, the innovative idea of simply drinking sodium bicarbonate solutions to induce minor changes in blood pH has been proposed.[21] This idea suffers from two major limitations. First, the pH change required to have significant effect on disrupting the RBD is likely to be too great to safely achieve in blood—a rule of thumb is at least 1 pH unit.[23] Second, even if this could be achieved the expression of ACEr is on the apical (lumen) surface of epithelial cells not the basolateral (plasma) side.[16] However, neither of these are problems for the kidney. Urine pH

is normally 5.5-6.5 (not too dissimilar to alveolar fluid—6.4-6.8[24]) and can be easily and safely manipulated. In fact, urine alkalinization protocols have been used for decades to reduce renal toxicity from various compounds (especially chemotherapy) and are recommended by US and European toxicology societies.[25] Here, the strategy will be deployed not for ion trapping but to inhibit the virus from infecting RTEC. Alkalizing the urine using IV sodium-bicarbonate solution to pH of 7.5 or more can be easily and safely achieved. Acetazolamide can also be added if systemic alkalemia is an issue.[25] An additional advantage of this approach is that it is unlikely to interfere with other interventions that can be studied in these patients (e.g. steroids) which are directed at the lungs.

5. Approach

We will conduct a pragmatic RCT using alkalinization of urine such that most ICU COVID-19 positive patients can be enrolled. Both specific aims will be achieved by the conduct of the trial yet both are independent. The statistical analysis plan for each aim will detail the specific endpoints and hypotheses being testing.

Trial overview: Study inclusion and exclusion criteria are provided in Table 1.

Study design: Open-label randomized trial (1:1) comparing urine alkalinization to standard care. The study will test both feasibility and safety (aim 1) as well as efficacy (aim 2).

Study Management: Study personnel will identify patients and obtain video-enabled informed consent from patients or legally authorized representatives; collect study data and ensure sample collection, processing and storage. The patient's bedside nurse will perform urine pH measurement (dipstick) and deliver the study drug. The study is open-label to facilitate safety and allow for any management of complications (e.g. calcium supplementation).

Table 1. Inclusion/exclusion Criteria

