Avoid fluid accumulation. If urine output does not increase to compensate for the increased fluid (it will in most cases, especially if kidney is protected), Lasix or Diamox can be added.
*If fluid balance cannot be maintained within +1L in 24 hours – protocol will be halted and resumed only if either the fluid balance can be correct to within +500mL in 24 hours or if the primary team decides that the patient has clinically appropriate fluid balance.

Data

collection: Information will be collected about patient demographics – date of birth, age, sex, race, weight, height, co-morbidities including but not limited to diabetes, hypertension, heart failure, coronary artery disease, previous cardiac surgeries, chronic kidney disease, cancers. Given the long history and familiarity with urine alkalinization, potential adverse effects (e.g. metabolic alkalosis, hypocalcemia) are well known. Data about renal function (creatinine, urine output, daily ins and outs), basic metabolic panel, blood gas, home medications, medications given during hospital stay and chart review to identify any relevant complications will also be performed. The provider survey will be performed using an online survey instrument and a link will be emailed to the provider to complete.

Sample collection: We will collect urine samples (1 before, 1 at 24 hours and 1 at 48 hours) from initiation of the protocol. Urine samples will be collected, processed and stored in accordance

with EH&S requirements for COVID-19 samples. At a later date and using alternative funding, we plan to analyze these samples for additional biomarkers either at WVU or at partner institution(s) in that study.[26] These biomarkers measure the cellular stress in the kidney[27] and will be examined in an ancillary study. The samples will be stored initially at the laboratories in WVU and then shipped to partner institution(s) for further testing of urine biomarkers as detailed above.

Statistical analysis: Descriptive statistics will be used for reporting: continuous variables expressed as median and interquartile range while categorical variables as frequency and percentages. No imputation will be performed and missing data will be treated as missing.

Aim 1: To determine feasibility and safety of a pragmatic urine alkalinization protocol for the prevention of AKI

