Primary feasibility outcome will be the proportion of patients treated who achieve >50% of urine measurements pH \geq 7.2 over the duration of treatment. Following specific adverse events will be monitored – hypokalemia (K<3.0meq/L), hypocalcemia (Ca<7.6mg/dL when corrected for albumin), Hypernatremia (Na>155meq/L), Volume overload (gaining weight >10% from admission weight during the protocol time-period, need for positive pressure ventilation or intubation due to volume overload), arrhythmias due to hypokalemia or hypocalcemia. To assess safety and feasibility, summary statistics including frequency, mean, standard deviation, median and interquartile range will be provided as applicable. Baseline data will be summarized comparing treatment groups over time. Chi-square/t-test will be used to compare the difference between treatment groups. Mixed model /ANCOVA will be used for repeated measurements over time.

As per the requirements of COE, a Data Safety Monitoring Board (DSMB) has been established that includes [name] [name], [name], [name] and [name] [name]. The DSMB will meet to review any adverse events after 5 and 25 patients have been recruited. In addition, as per the requirements of COE, the DSMB will meet to review any adverse events after the first 5 patients randomized to the interventional drug (open label arm) have been recruited and completed the study.

Aim 2: To determine the efficacy of urine alkalinization for prevention of AKI

Primary efficacy outcome will be the number of days alive and free of stage 2-3 AKI (up to 28) in each group. Secondary endpoints will include the proportion of patients developing stage 2-3 AKI (or stage 3 if already at stage 2 at enrollment); ventilator-free days to 28 and hospital-free days to 60. For AKI-free, ventilator-free, and hospital-free days, zero truncated negative binomial models will be implemented.

Severe AKI will be considered as binary outcome. Multivariable logistic regression will be used to assess the overall odds associated with treatment adjusted by baseline covariates (age, demographics, baseline renal function). Random forest decision tree regression method will be implemented to assess patient variable importance towards the outcome. Hazard will be assessed using cox proportional hazard model.

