Sample size determination: The study will be powered to achieve a 50% increase in the number of days alive and free of stage 2-3 AKI to day 28. We hypothesis an increase from 10 +/- 5 days to 15 +/- 5 days. The sample size needed to achieve this difference is 16 patients per group. We plan to enroll 20 patients per group for a total sample size of 40 patients. [name], Professor of Critical Care Medicine at the University of Pittsburgh and a co-investigator on this application is working towards a similar trial at the University of Pittsburgh (see attached letter of

support). The results from both these studies will then be pooled and changes in AKI rates, and survival will be examined.

Relevance to the current COVID-19 pandemic

There are at least four reasons why this study will have an important impact. First, when severe AKI does occur, mortality is very high.[6, 7] Preventing early AKI may reduce severe AKI as the disease progresses. Second, AKI has considerable effects on the immune system reducing a variety of immune functions[28] and hence might contribute to reduced host response. Third, this is unlikely to be the last β-coronavirus outbreak and different strains may cause even more AKI. Finally, the results of this study would provide critical proof of concept data that could be used to design other therapies to reduce viral RBD affinity. For example, alveolar pH could also be manipulated. Showing feasibility with this safe and available strategy could be the first step toward other related efforts.

C. REFERENCES

2. **KDIGO Clinical Practice Guideline for Acute Kidney Injury** [<https://kdigo.org/wp-content/uploads/2016/10/KDIGO-2012-AKI-Guideline-English.pdf>]

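### The AKI logistic model has at most about four limiting outcomes per term and no fallback; a penalised fit with a fixed covariate list would be safer

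*Combined protocol and SAP*

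**What the plan says.** Under Statistical analysis, Aim 2, the binary analysis opens with "Severe AKI will be considered as binary outcome". The model follows: "Multivariable logistic regression will be used to assess the overall odds associated with treatment", "adjusted by baseline covariates (age, demographics, baseline renal function"). Severe AKI is not defined. The listed secondary endpoint is "the proportion of patients developing stage 2-3 AKI (or stage 3 if already at stage 2 at enrollment").

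Demographics are not defined as model terms. The nearest guide is the data collection paragraph, which lists "date of birth, age, sex, race, weight, height" among the items recorded. On size, Sample size determination says "We plan to enroll 20 patients per group for a total sample size of 40 patients", and the study design is an "Open-label randomized trial (1:1) comparing urine alkalinization to standard care". Missing values are not to be imputed, so the model may be fitted to fewer than 40 patients.

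The plan gives no expected event count for this model, no coding of the covariates, no limit on their number, and no penalised, exact or fallback method. Of AKI at any stage, the Background says "It has been described to be present among 15-25% patients with COVID-19". It also gives a figure of over 50% for critically ill patients in general. The Significance section adds that most COVID-19 AKI is mild to moderate.

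**The concern.** Logistic regression draws its information from the rarer of the two outcomes. With few such outcomes per term, ordinary maximum likelihood has two known weaknesses. A covariate pattern may separate events from non-events, so that some coefficient has no finite estimate. When all estimates are finite, a real effect is on average reported as larger than it is.

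This is the only model in the plan said to produce a treatment odds ratio for AKI. The trial is open-label and no fallback is named, so a failed fit would leave covariates to be dropped or merged after the data have been seen. The AKI results are also meant to be pooled with a second centre.

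**Working it through.** **The plan's own figure.** The only sizing calculation concerns AKI-free days, 10 versus 15 with SD 5. Assuming two-sided 5% and 80% power (neither is stated), n = 2 × (1.96 + 0.84)² × 5²/5² = 15.7, or 16 per group, as the plan says. It has no bearing on the logistic model, for which the plan gives no figure.

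**Number of terms.** Treatment + age + sex + race (two levels) + one renal measure = 5. If demographics means sex only, the count is 4. More race levels raise it.

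**Limiting outcomes.** The ceiling is 40/2 = 20, whatever the event rate.

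| Assumed event rate | Events of 40 | Per term, 5 terms | Per term, 4 terms |
|---|---|---|---|
| 15% | 6 | 1.2 | 1.5 |
| 25% | 10 | 2.0 | 2.5 |
| 50% | 20 | 4.0 | 5.0 |

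Above 50% the non-events become the limit and the ratio falls again.

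**Separation.** Trials of 20 per arm were simulated with the five terms. Age and renal function were standard normal with log odds ratios of 0.5 and 0.7 per SD, and sex was split evenly. Separation was detected by linear programming. The covariate effects and race shares are assumptions; the documents give neither. The table shows the share of trials with no finite estimate for at least one coefficient when treatment has no effect.

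| Minority race share | 15% rate | 25% rate | 50% rate |
|---|---|---|---|
| 15% | 44% | 26% | 9% |
| 30% | 27% | 7% | 0% |
| No race term | 15% | 2% | 0% |

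With a true OR of 0.4, a 15% race share and control-arm rates of 15%, 25% and 50%, the shares are 66%, 38% and 12%. Without the race term they are 38%, 10% and 0%.

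The treatment coefficient itself was infinite less often. With moderate covariate effects and true ORs from 1 to 0.25, this happened in 10-25% of trials at about 6 events, 1-6% at 10 and 0-0.2% at 20.

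**Size of the estimate when all coefficients are finite.** For a true OR of 0.4 the log OR is ln 0.4 = -0.92. The mean estimate was 17-32% too large, at race shares of 15% and 30%:
- -0.92 × 1.17 = -1.07, an OR of about 0.34;
- -0.92 × 1.32 = -1.21, an OR of about 0.30.

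Medians were less inflated than means. With a true OR of 1, medians lay between -0.08 and +0.08, but 41-58% of finite odds ratios fell outside 0.5 to 2.

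**Firth with the same five terms.** For a true log OR of -0.92 the mean was -0.87 to -0.95, that is 0.87/0.92 = 95% to 0.95/0.92 = 103% of the truth. With no effect and a 10% race share, the SD of the treatment log OR was 1.07 against 1.58 for ordinary maximum likelihood at a 15% event rate, and 0.73 against 0.91 at 50%. Firth estimates were finite whenever both outcomes occurred.

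**The case against.** The strongest reply is that separation here is largely a nuisance-covariate problem. Much of it comes from an assumed sparse race indicator, and the documents neither give race shares nor say that race enters the model. This stands. A reader might infer that the treatment odds ratio will often be inestimable; above about 10 events that is seldom so.

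A reader might also infer that the model exaggerates treatment benefit whatever the truth. It does not: the bias needs a true effect and is modest beside the sampling error. Nor is there ground for calling the intervals misleading. Among finite fits, nominal 95% Wald intervals covered 94-99% and null rejection was 2-6%. They are wide, and the weakness lies in estimation and convergence rather than in false positives.

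The range of 6 to 20 events is not a forecast from the plan. It applies background any-stage rates to an outcome of stage 2-3 or severe AKI, for which the count could be lower. The assumed 10 AKI-free days of 28 in the control group point instead to far more AKI or death than 15-25%. A rate above 50% would make non-events scarce, so the ceiling of 20 holds either way.

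Finally, this is a secondary analysis, and the primary outcome and sample size do not depend on it. That limits the priority of the change but does not argue against making it.

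**Conclusion.** The concern holds in a limited form. With five terms the plan allows at most 4 limiting outcomes per term, and 1.2 to 2 if the 15-25% background rates carry over. At 6-10 events, separation of some coefficient ranged from 7% to 44% of trials with no effect and a two-level race term at a 15-30% share. It was higher with a real effect and lower without a race term. Near 20 events it was 0-9%. A true OR of 0.4 would be reported on average as about 0.30 to 0.34 when the fit is finite. These percentages rest on the assumed covariate effects and race shares; the ceiling of 20 limiting outcomes does not.

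The planned pooling with a second centre has no stated size and does not alter the 40-patient analysis. The primary efficacy conclusion is not at risk. The change is worth making because it is cheap and because the plan names no safeguard.

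**What to change.** In the Aim 2 analysis text:

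1. Replace ordinary maximum likelihood with Firth-penalised logistic regression and profile-likelihood intervals.
2. Fix a short covariate list and its coding in advance, for example treatment, age, sex and one named baseline renal measure. Collapse any race term to two levels. The bias argument does not require dropping age or demographics, since the five-term Firth fit was already close to unbiased. The purpose of the list is to avoid sparse cells and choices made after seeing the data.
3. Report the unadjusted risk difference with its 95% CI beside the odds ratio.
4. Apply both to the listed secondary AKI endpoint and remove the undefined severe AKI.

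The cost is a few lines of SAP text and standard software. The downsides are slight shrinkage and a less detailed demographic adjustment. The change does not create precision. With 25% events in both arms, the risk difference has a standard error of √(2 × 0.25 × 0.75/20) = 0.137, so its 95% interval is about ±27 percentage points (1.96 × 0.137 = 0.27).
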